#### **3.2 Exclusion Criteria**

3.2.1 History of allergic reactions attributed to heparin or low molecular weight heparin

- 3.2.2 Active bleeding or otherwise considered high risk for hemorrhage (e.g. known acute gastrointestinal ulcer)
- 3.2.3 Any history of significant hemorrhage (requiring hospitalization or transfusion) within the last 6 months (excluding hemorrhage during operative procedure).
- 3.2.4 History of heparin induced thrombocytopenia
- 3.2.5 Presence of coagulopathy (PT or PTT > 1.2 x upper limit of normal)
- 3.2.6 Known diagnosis of disseminated intravascular coagulation
- 3.2.7 Currently receiving therapeutic anticoagulant therapy or dual antiplatelet therapy (eg. aspirin and clopidogrel)
- 3.2.8 Uncontrolled arterial hypertension (systolic blood pressure > 200mmHg, diastolic >110mmHg)
- 3.2.9 Active peptic ulcer disease
- 3.2.10 Bacterial endocarditis
- 3.2.11 Received any type of pharmacologic thromboprophylaxis (e.g. low molecular weight heparin or heparin) for >48 hours during current hospitalization
- 3.2.12 Known brain metastases

### **3.3 Inclusion of Women and Minorities**

Both men and women of all races and ethnic groups are eligible for this trial.

## **4. REGISTRATION PROCEDURES**

### **4.1 General Guidelines for DF/HCC and DF/PCC Institutions**

Institutions will register eligible participants with the DF/HCC Quality Assurance Office for Clinical Trials (QACT) central registration system. Registrations must occur prior to the initiation of protocol therapy. Any participant not registered to the protocol before protocol therapy begins will be considered ineligible and registration will be denied.

An investigator will confirm eligibility criteria and a member of the study team will complete the QACT protocol-specific eligibility checklist.

Following registration, QACT office will perform randomization to Arm A or Arm B of enoxaparin. Randomization arm will be communicated directly through QACT to the research pharmacy at Beth Israel Deaconess Medical Center. For participants enrolled at Cleveland Clinic, a representative from the BIDMC Research Pharmacy will forward the randomization assignment to the dedicated contact at the Cleveland Clinic Research Pharmacy.

Issues that would cause treatment delays should be discussed with the Overall Principal Investigator (PI). If a participant does not receive protocol therapy following registration, the participant's registration on the study must be canceled. Notify the QACT Registrar of registration cancellations as soon as possible.

#### **4.2 Registration Process for DF/HCC and DF/PCC Institutions**

The QACT registration staff is accessible on Monday through Friday, from 8:00 AM to 5:00 PM Eastern Standard Time.

The registration procedures are as follows:

- Obtain written informed consent from the participant prior to the performance of any protocol specific procedures or assessments.
- Complete the QACT protocol-specific eligibility checklist using the eligibility assessment documented in the participant's medical record and/or research chart. **To be eligible for registration to the protocol, the participant must meet all inclusion and exclusion criterion as described in the protocol and reflected on the eligibility checklist.**
- Fax the eligibility checklist(s) and all pages of the consent form(s) to the QACT at xxx-xxx-xxxx. For Phase I protocols, attach participant dose level assignment confirmation from the sponsor.
- The QACT Registrar will (a) review the eligibility checklist, (b) register the participant on the protocol, and (c) randomize the participant when applicable.
- An email confirmation of the registration and/or randomization will be sent to the Overall PI, research pharmacy, study coordinator(s) from the Lead Site, treating investigator and registering person immediately following the registration and/or randomization.

#### **4.3 General Guidelines for Other Investigative Sites**

Eligible participants will be entered on study centrally at Beth Israel Deaconess Medical Center by the Study Coordinator.

Following registration, participants should begin protocol therapy within 24 hours. Issues that would cause treatment delays should be discussed with the Overall PI. If a participant does not

receive protocol therapy following registration, the participant's registration on the study must be canceled and they will be replaced. The Study Coordinator should be notified of cancellations as soon as possible.

#### **4.4 Registration Process for Other Investigative Sites**

To register a participant, the following documents should be completed by the research nurse or data manager and sent to::

- Copy of eligibility documentation
- Signed eligibility and consent physician note
- Signed participant consent form
- HIPAA authorization form
- Eligibility Checklist

The research nurse or data manager at the participating site will then call xxx-xxx-xxxx or e-mail to verify eligibility. To complete the registration process, the Coordinator will

- register the participant on the protocol with the QACT
- fax or e-mail the participant study number, and if applicable the dose treatment level to the participating site
- call the research nurse or data manager at the participating site and verbally confirm registration

**NOTE: Registration and randomization with the QACT can only be conducted during the business hours of 8:00 AM and 5:00 PM Eastern Standard Time Monday through Friday.**  
Same day treatment registrations will only be accepted with prior notice and discussion with the DF/HCC Lead Institution.

### **5. TREATMENT PLAN**

#### **5.1 Treatment Regimen**

##### **Treatment Overview:**

Eligible participants will be randomized to standard dose enoxaparin at 40 mg once daily (Arm A) versus weight-based enoxaparin at 1 mg/kg once daily (Arm B). On study enoxaparin will be administered for up to 14 days during hospitalization. Physicians and participants will be double-blinded to enoxaparin dosing during hospitalization (or up to 14 days). After the day 14 assessment, treatment arms will be un-blinded in order to appropriately schedule a bilateral lower extremity ultrasound for participants enrolled onto Arm A at day 17.

Note that patients who are discharged and re-admitted prior to day 14 will resume study procedures and enoxaparin administration per initial randomization.

##### **Arm A:**

Participants will receive enoxaparin 40 mg subcutaneously once daily.

**Arm B:**

Participants will receive enoxaparin at 1mg/kg subcutaneously once daily with maximum dose of 100 mg daily. Participants who weigh more than 100kg will be capped at 100mg.

Participants who receive at least one dose of treatment post-randomization will be considered evaluable for the study.

**5.2 Pre-Treatment Criteria**

In order to proceed with day 1 administration of enoxaparin, platelet count must be  $\geq 50,000/\mu\text{l}$  and CrCl must be  $>/= 50 \text{ ml/min}$ . All other laboratory assessments performed within 48 hours of enrollment may be used to determine eligibility and do not need to be repeated.

**5.2.1 Cycle 1, Day 1**

Enoxaparin syringe will be dispensed by research pharmacy. Baseline assessments for symptoms of VTE or hemorrhage will be recorded. All doses of enoxaparin will be recorded along with time of administration.

**5.2.2 Day  $7 \pm 1$  days**

Enoxaparin will be ordered on a daily basis and study labs will be continued for those study subjects who remain hospitalized. Assessment for evidence of major hemorrhage or VTE will be recorded by study staff if the participant remains hospitalized.

**5.2.3 Day 14 -4, + 7 days**

Enoxaparin should be continued until either hospital discharge or day 14. After receiving the final dose of enoxaparin no additional doses of enoxaparin on study will be administered. Assessment for evidence of major hemorrhage or VTE will be recorded. After the day 14 clinical assessment, study staff will become unblinded to treatment allocation in order to appropriately schedule a bilateral lower extremity ultrasound for study subjects on Arm A (see 5.3 below). For participants who remain hospitalized, study subjects should continue with standard pharmacologic thromboprophylaxis per the discretion of the treating physician. Day 14 symptom assessment can be performed by phone.

**5.3 Off treatment procedures (unblinding)**

Following the completion of the day 14 assessment, study staff will contact a clinical research pharmacist at BIDMC. Criteria for off treatment will be reviewed and then the study staff will be informed as to whether the participant was previously assigned to Arm A (standard enoxaparin) versus Arm B (weight-based enoxaparin). For participants randomized to Arm A, a bilateral ultrasound will be scheduled (see study calendar) to evaluate for asymptomatic deep vein thrombosis.

#### **5.4 Agent Administration**

The concentration of enoxaparin is 100 mg/ml. All enoxaparin doses will be diluted to 1 ml final volume such that neither the healthcare providers nor the participant are readily able to identify dosage. Subcutaneous enoxaparin administration may be alternated between the left and right anterolateral and left and right posterolateral abdominal wall once daily.

#### **5.5 General Concomitant Medication and Supportive Care Guidelines**

The use of growth factors will be recorded. Subject must be taken off protocol if requires therapeutic anticoagulation or dual antiplatelet agents (eg. aspirin and clopidogrel)

#### **5.6 Criteria for Taking a Participant Off Protocol Therapy**

Cessation of enoxaparin and withdrawal from the study is mandated for the following reasons:

- Grade 3 or 4 hemorrhage and/or
  - Symptomatic hemorrhage in a critical area or organ such as intracranial, intraspinal, intraocular, retroperitoneal, intra-articular or pericardial, or intramuscular with compartment syndrome, and/or hemorrhage causing an acute fall in hemoglobin  $\geq 2\text{g/L}$  or hemorrhage leading to a transfusion of  $\geq 2$  units of packed red blood cells.
- Development of confirmed heparin induced thrombocytopenia
- Proximal deep vein thrombosis or pulmonary embolism
- Condition requiring therapeutic anticoagulation or dual antiplatelet therapy
- Renal failure (see section 6)
- Participant decides to withdraw from the protocol therapy
- General or specific changes in the participant's condition render the participant unacceptable for further treatment in the judgment of the treating investigator

Participants will be removed from the protocol therapy when any of these criteria apply. The reason for removal from protocol therapy, and the date the participant was removed, must be documented in the case report form (CRF). Alternative care options will be discussed with the participant.

A QACT Treatment Ended/Off Study Form will be filled out when a participant is removed from protocol therapy. This form can be found on the QACT website or obtained from the QACT registration staff.

In the event of unusual or life-threatening complications, treating investigators must immediately notify the Overall PI:

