### **5.7 Duration of Follow Up**

Participants will be followed until last scheduled protocol visit. Participants removed from protocol therapy for unacceptable adverse event(s) will be followed until resolution or stabilization of the adverse event. Participants who have ongoing related adverse events at the last visit will be followed until resolution of those adverse events.

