### **5.8 Criteria for Taking a Participant Off Study**

Participants will be removed from study when any of the following criteria apply:

- Lost to follow-up
- Withdrawal of consent for data submission
- Death

The reason for taking a participant off study, and the date the participant was removed, must be documented in the case report form (CRF).

A QACT Treatment Ended/Off Study Form will be filled out when a participant comes off study. This form can be found on the QACT website or obtained from the QACT registration staff.

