### **Renal Failure**

CrCl (ml/min)	Arm A (standard enoxaparin)	Arm B (adjusted dose enoxaparin)
>40	No change	No change
30-40	No change	DECREASE to 40 mg daily
<30	HOLD	HOLD

Creatinine will be monitored at each study visit and as part of routine medical care. Enoxaparin

will be held for acute renal failure ( $\text{CrCl} < 30 \text{ml/min}$ ) diagnosed at any point during the study.

*Enoxaparin should be resumed when  $\text{CrCl}$  improves to  $\geq 40 \text{ml/min}$ .*

The  $\text{CrCl}$  can be estimated by either the Modification of Diet in Renal Disease (MDRD) which can be found at [http://www.kidney.org/professionals/KLS/gfr\\_calculator.cfm](http://www.kidney.org/professionals/KLS/gfr_calculator.cfm) or Cockcroft-Gault equation (below)

Men:

$$\text{CrCr (mL/min)} = \frac{(\text{140} - \text{age}) \times \text{body weight [kg]}}{\text{Cr [mg/dL]} \times 72}$$

Women:  $\text{CrCl (mL/min)} = \text{CrCl (as above)} * 0.85$

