### 13.7.2 Evaluation of the Primary Efficacy Endpoint

All participants will be assessed for primary endpoints as long as received at least 1 dose of enoxaparin following randomization.

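### The lead sentence of section 5.6 couples stopping enoxaparin with leaving the study, against sections 5.7, 5.8, 6 and 13.7.2; if followed literally, it could cost endpoint assessments.

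*Combined protocol and SAP*

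**What the plan says.** All references are to the combined protocol and SAP.

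- **5.6, lead sentence:** "Cessation of enoxaparin and withdrawal from the study is mandated for the following reasons". The list covers Grade 3 or 4 or otherwise serious hemorrhage, confirmed heparin-induced thrombocytopenia, "Proximal deep vein thrombosis or pulmonary embolism", a condition needing therapeutic anticoagulation or dual antiplatelet therapy, renal failure (with a pointer to section 6), the participant's decision to stop, and the investigator's judgment.
- **5.6, heading and closing text:** both concern protocol therapy. After the list: "Participants will be removed from the protocol therapy when any of these criteria apply". Study withdrawal is not repeated.
- **5.7:** "Participants will be followed until last scheduled protocol visit". No exception is made for participants who are off drug.
- **5.8:** "Participants will be removed from study when any of the following criteria apply". The list is loss to follow-up, withdrawal of consent for data submission, and death.
- **Section 6, Renal Failure:** drug is held below a creatinine clearance of 30 mL/min. Then "Enoxaparin should be resumed when" clearance is back to at least 40 mL/min.
- **Section 6, Hemorrhage:** Grades 3 and 4 mean off protocol therapy. Leaving the study is not mentioned.
- **13.7.2:** "All participants will be assessed for primary endpoints as long as received at least 1 dose of enoxaparin following randomization".
- **5.5:** a subject who needs therapeutic anticoagulation or dual antiplatelet agents comes off protocol. The text does not say whether that means drug, follow-up or both.

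**The concern.** The lead sentence of 5.6 attaches two mandatory consequences to each listed reason: the drug stops and the participant leaves the study. The second cannot be squared with 5.7, 5.8 or 13.7.2. For renal failure, a participant withdrawn from the study cannot also resume drug as section 6 provides.

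The purpose of the trial is to produce point estimates for planning a phase III trial (13.2, 13.4). The primary analysis in 13.5 is an exact binomial proportion, VTE at day 17 in Arm A and major hemorrhage at day 14 in both arms, and the plan has no rule for a dosed participant who was not assessed. Asymptomatic DVT in Arm A is sought by one scheduled ultrasound, so a participant who leaves before it loses that chance of detection. With 25 in an arm, each unassessed participant is 1/25 = 4 percentage points of uncertainty. Two sites are taking part and could read 5.6 differently.

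**Working it through.** **Step 1. Which texts conflict with study withdrawal.**

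| Text | Consequence stated | Agrees with study withdrawal? |
|---|---|---|
| 5.6 lead sentence | Stop drug and leave study | It is the source |
| 5.6 heading and closing text | Off protocol therapy | No |
| 5.7 | Follow to last planned visit | No |
| 5.8 | Off study for three reasons, none of them a 5.6 clinical trigger | No |
| Section 6, Renal Failure | Hold, then resume | No |
| Section 6, Hemorrhage, Grades 3 and 4 | Off protocol therapy | No |
| 13.7.2 | Everyone with at least one dose is assessed | No |

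The conflict over the drug rule itself is confined to renal failure. For Grade 3 or 4 hemorrhage and for heparin-induced thrombocytopenia, section 6 agrees with 5.6 that drug stops. Section 6 has no rule for VTE, so for VTE the conflict is with 5.7, 5.8 and 13.7.2.

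**Step 2. What a literal reading could lose.**

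- *Proximal DVT or PE:* already a primary VTE event under section 11. Only the later hemorrhage assessment is at risk.
- *Hemorrhage meeting the section 11 definition:* that endpoint has already occurred. The rest of the VTE assessment is at risk, including the Arm A ultrasound.
- *Renal failure, heparin-induced thrombocytopenia, a condition needing anticoagulation or dual antiplatelet therapy, or a participant's or investigator's decision:* both endpoints could go unassessed.

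**Step 3. Reproduce the plan's interval.** Inputs from 13.2: 25 participants in Arm A and 12% incidence, so x = 3 and n = 25. The exact (Clopper-Pearson) 90% limits are

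- lower = 5th percentile of Beta(x, n − x + 1) = Beta(3, 23) → 3.35%
- upper = 95th percentile of Beta(x + 1, n − x) = Beta(4, 22) → 28.17%

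The plan states 3.3 to 28.2%. This reproduces, with the lower limit truncated rather than rounded.

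**Step 4. Size of the possible loss.** The documents give no expected number meeting a 5.6 criterion. Assume 3 VTE are seen and w of the 25 Arm A participants leave unassessed without an observed VTE, with w from 1 to 5. Three ways of handling them:

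- kept in the denominator as event-free: 3/25 = 12.0% (3.4 to 28.2%) for every w
- dropped: 3/(25 − w)
- all had a VTE (the extreme case): (3 + w)/25

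| w | Dropped (90% CI) | All had a VTE (90% CI) |
|---|---|---|
| 1 | 3/24 = 12.5% (3.5 to 29.2) | 4/25 = 16.0% (5.7 to 33.0) |
| 2 | 3/23 = 13.0% (3.7 to 30.4) | 5/25 = 20.0% (8.2 to 37.5) |
| 3 | 3/22 = 13.6% (3.8 to 31.6) | 6/25 = 24.0% (11.0 to 42.0) |
| 4 | 3/21 = 14.3% (4.0 to 32.9) | 7/25 = 28.0% (13.9 to 46.2) |
| 5 | 3/20 = 15.0% (4.2 to 34.4) | 8/25 = 32.0% (17.0 to 50.4) |

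If 13.7.2 governs and follow-up is complete, w = 0 and the planned estimate is unaffected.

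**The case against.** The strongest reply is that the protocol already separates the end of drug from the end of follow-up, and that one loose phrase should not outweigh the rest. Section 5.7 makes no exception for being off drug. Under the study calendar drug stops at discharge or day 14, yet only the day-7 visit is waived after discharge. The day-14 symptom assessment may be done by telephone (5.2.3). Section 5.3 schedules the ultrasound for those randomized to Arm A, with no condition that they still be on drug. The pointer in the 5.6 renal entry can also be read as deferring to section 6, and 5.6 does not call the cessation permanent.

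Most of this stands. It makes off therapy only the likely intent, so loss of assessments is a possibility and not an established consequence. It does not remove the contradiction: study withdrawal is still mandatory in 5.6, 5.5 is loose in the same way, one form serves for both treatment ended and off study, and no text sets precedence. The renal pointer allows the deferring reading but does not state it.

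A reader might go further and infer that 5.6 takes the highest-risk patients out of endpoint assessment. The documents do not support that. Those with proximal DVT or PE, or qualifying major hemorrhage, have already had that endpoint, and nothing shows that the others are the highest-risk group.

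It is also fair that dropping the unassessed moves the estimate little (12.0% to between 12.5% and 15.0%) against a planned interval about 25 points wide, and that the upper figures require every unassessed participant to have had a VTE.

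**Conclusion.** The point holds as an internal contradiction with a conditional consequence. The 5.6 lead sentence conflicts with the rest of 5.6 and with 5.7, 5.8, the hemorrhage table in section 6 and 13.7.2, and its renal entry has to be reconciled with section 6. No figure in the plan is wrong because of it.

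If a site applied the sentence literally, with 3 VTE seen, the Arm A day-17 estimate could lie anywhere from 12% to 16% with 1 participant unassessed, to 24% with 3, or to 32% with 5. These ranges rest on an assumed number unassessed and on the extreme that all or none of them had a VTE. A reader might infer a definite downward bias. That would need the unassessed to be counted as event-free and some of them to have had undetected events, and 13.5 does not say how they are counted. The matter still merits an amendment, because the rule is written as mandatory, the estimates are the trial's product, and the correction is small.

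**What to change.** 1. In the lead sentence of 5.6, delete the words that add study withdrawal to stopping drug.
2. Add to 5.6 that participants off protocol therapy, unless off study under 5.8, keep the day-14 assessment and, in Arm A, the day-17 ultrasound.
3. In 5.5, make the same distinction between coming off drug and leaving follow-up.
4. Reconcile the renal entry in 5.6 with the hold-and-resume rule in section 6. Which drug rule applies is for the sponsor's clinicians.

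The cost is a wording amendment and a note to the two sites. The assessments are already in the study calendar, so no new procedure is added. The documents do not say how the visits and scans are funded.

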### **5.7 Duration of Follow Up**

Participants will be followed until last scheduled protocol visit. Participants removed from protocol therapy for unacceptable adverse event(s) will be followed until resolution or stabilization of the adverse event. Participants who have ongoing related adverse events at the last visit will be followed until resolution of those adverse events.

### **5.8 Criteria for Taking a Participant Off Study**

Participants will be removed from study when any of the following criteria apply:

- Lost to follow-up
- Withdrawal of consent for data submission
- Death

The reason for taking a participant off study, and the date the participant was removed, must be documented in the case report form (CRF).

A QACT Treatment Ended/Off Study Form will be filled out when a participant comes off study. This form can be found on the QACT website or obtained from the QACT registration staff.

## **6. DOSING DELAYS/DOSE MODIFICATIONS**

Dose delays and modifications will be made as indicated in the following table(s). The descriptions and grading scales found in the revised NCI Common Terminology Criteria for Adverse Events (CTCAE) version 4.0 will be utilized for dose delays and dose modifications. A copy of the CTCAE version 4.0 can be downloaded from the CTEP website [http://ctep.cancer.gov/protocolDevelopment/electronic\\_applications/ctc.htm](http://ctep.cancer.gov/protocolDevelopment/electronic_applications/ctc.htm).

### **Renal Failure**

CrCl (ml/min)	Arm A (standard enoxaparin)	Arm B (adjusted dose enoxaparin)
>40	No change	No change
30-40	No change	DECREASE to 40 mg daily
<30	HOLD	HOLD

Creatinine will be monitored at each study visit and as part of routine medical care. Enoxaparin

will be held for acute renal failure ( $\text{CrCl} < 30 \text{ml/min}$ ) diagnosed at any point during the study.

*Enoxaparin should be resumed when  $\text{CrCl}$  improves to  $\geq 40 \text{ml/min}$ .*

The  $\text{CrCl}$  can be estimated by either the Modification of Diet in Renal Disease (MDRD) which can be found at [http://www.kidney.org/professionals/KLS/gfr\\_calculator.cfm](http://www.kidney.org/professionals/KLS/gfr_calculator.cfm) or Cockcroft-Gault equation (below)

Men:

$$\text{CrCr (mL/min)} = \frac{(\text{140} - \text{age}) \times \text{body weight [kg]}}{\text{Cr [mg/dL]} \times 72}$$

Women:  $\text{CrCl (mL/min)} = \text{CrCl (as above)} * 0.85$

